3.3.2 Handling of Missing Data

Missing values will not be imputed.

3.3.3 Planned Interim Analysis

An interim analysis may be conducted after at least 50% of the subjects have been enrolled.

3.4 Demographic and Baseline Characteristics

Demographic and Baseline characteristics (e.g., age, gender, ethnicity, race, weight, height, BMI, and CVD risk) will be summarized using descriptive statistics by treatment group.

BMI will be computed using the formula: $BMI = (\text{weight in kilograms}) / [\text{height in cm} / 100]^2$

Subject randomization and disposition will be summarized by treatment group. All subjects enrolled will be included in the summary.

Protocol deviations will be listed.

3.5 Efficacy Analysis

3.5.1 Primary Efficacy Analysis

The primary analysis will be the comparison of percent change from Baseline to Study Week 7 (Study Day 43) in plasma AGT between ISIS 757456 80 mg group and placebo group in PPS. The data will be analyzed using analysis of variance (ANOVA) with treatment and randomization stratification factor (screening AGT concentration) as independent variables. The normality assumption for the ANOVA model will be assessed by the Shapiro-Wilks test on the residuals. In the case data departs substantially from normality, the nonparametric van Elteren test will be employed instead.

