3. EXPERIMENTAL PLAN

3.1. Study Design

This will be a Phase 2, double-blind, randomized, placebo-controlled study of ISIS 757456 conducted in mild hypertensive subjects on an ACEi/ARB and an additional hypertensive medication (see Section 5.1 Inclusion Criteria). Subjects will be stratified based on a screening plasma AGT concentration ($\leq 30 \mu\text{g/mL}$ vs. $> 30 \mu\text{g/mL}$) and randomized in a 2:1 ratio to receive a once-weekly SC treatment and an additional loading dose on Study Day 3 with either ISIS 757456 80 mg or placebo for 6 weeks (See [Study Design and Treatment Schema](#)).

All subjects will complete a 13-week Post-Treatment Period. In the Post-Treatment Period, should a subject's sitting BP on home monitoring exceed 140 mmHg systolic or 100 mmHg diastolic on 2 consecutive days (confirmed by triplicate measurement at the Study Center), the subject's initial HTN medication(s) may be added back per Investigator and Sponsor Medical Monitor judgment and the subject will continue to be followed per protocol in the study.

Refer to Section 8.1 for additional details.

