3.3. Number of Subjects

Approximately 30 subjects are planned to be enrolled in this study.

The 80 mg once-weekly dose is designed to assess the safety, tolerability, and efficacy of Study Drug (ISIS 757456 or placebo) given over a 6-week period. An additional loading dose will be given on Study Day 3. The sample size was selected to ensure that the safety and tolerability of ISIS 757456 will be adequately assessed while minimizing unnecessary subject exposure.

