1.3 Endpoints

1.3.1 Primary Endpoint

- Percent change in plasma angiotensinogen from Baseline to Study Day 43 (Week 7) compared to placebo

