3 ANALYSIS PLAN

3.1 General Overview of Analyses

Descriptive summary statistics including number of subjects, mean, median, standard deviation, standard error of mean, 25th percentile, 75th percentile, minimum, and maximum for continuous variables, and counts and percentages for categorical variables will be used to summarize most data. All statistical tests will be conducted using 2-sided tests with 5% Type I error rate unless otherwise stated.

[figure not shown]
PK parameters will be summarized using include number of subjects, mean, standard deviation, coefficient of variation (CV), geometric mean, median, minimum, and maximum.

Baseline definition:

The baseline for plasma AGT will be define as the average of all values on or after Study Day -7 and prior to the first dose of Study Drug. The baseline for all other assessments will be defined as the last non-missing measurement prior to the first dose, unless otherwise specified.

Analytical visits:

Data will be summarized using the visit labels provided in the data. Multiple results with the same visit label will be averaged. Results with visit labels as "Unscheduled" will not be included in the by-visit summary tables and figures except for determining baseline and the analysis of confirmed ALT/AST category (see section 3.7.3) but will be presented in data listings.

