3.5.2 Secondary Efficacy Analyses

The secondary efficacy analyses will be performed in a similar way to the primary analysis, which include:

- Comparison of change and percent change from Baseline to each schedule post-Baseline visit in AGT between ISIS 757456 80 mg group and placebo group in PPS and FAS
- Comparison of change from Baseline to each schedule post-Baseline visit in in-clinic SBP and DBP between ISIS 757456 80 mg group and placebo group in PPS and FAS. Subsequent SBP and DBP measurements will be completely removed from this analysis once the subjects received first administration of antihypertensive therapy during the study.

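### The primary AGT analysis pools one variance across a 2:1 split, checks only normality, and may switch to a test with no specified between-arm estimate, so the precision of the estimated reduction is not secured

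*Combined protocol and SAP*

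**What the plan says.** The primary endpoint (SAP 1.3.1) is on the percent-change scale: "Percent change in plasma angiotensinogen from Baseline to Study Day 43 (Week 7) compared to placebo". For the Per Protocol Set, SAP 3.5.1 specifies its model as follows: "The data will be analyzed using analysis of variance (ANOVA) with treatment and randomization stratification factor (screening AGT concentration) as independent variables". Protocol 10.6.3 has the same model.

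One assumption is checked: "The normality assumption for the ANOVA model will be assessed by the Shapiro-Wilks test on the residuals". The consequence is: "In the case data departs substantially from normality, the nonparametric van Elteren test will be employed instead". No cut-off defines a substantial departure. Neither document mentions a check of equal variances, a robust or unequal-variance standard error, a confidence interval for the treatment difference, or an estimator to accompany van Elteren.

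SAP 3.5.2 carries this forward: "The secondary efficacy analyses will be performed in a similar way to the primary analysis". It covers AGT change and percent change at each post-baseline visit, in both the Per Protocol Set and the Full Analysis Set.

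On size, protocol 3.3 says "Approximately 30 subjects are planned to be enrolled in this study", and protocol 3.1 has them "randomized in a 2:1 ratio to receive a once-weekly SC treatment". SAP 3.1 plans means, SDs, standard errors, medians and quartiles for most data.

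**The concern.** An ANOVA with treatment and stratum estimates a single residual variance. When the arms differ in spread and in size, that pooled variance gives the wrong standard error for the difference: too small if the smaller arm is the more variable, too large if it is the less variable.

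Percent change makes unequal spread plausible here. It equals 100 x (Day 43 AGT / baseline AGT - 1), so if error is proportional to the level, the active arm's SD shrinks as AGT falls. Placebo, with about 10 subjects, would then be both smaller and more variable. The plan does anticipate AGT lowering: the amendment's rationale for the blood pressure rules in section 8.5.3 refers to it.

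The normality gate adds a second problem. A mixture of two spreads can look non-normal, so the switch becomes more likely when the drug works well, and the plan then names no between-arm estimate. AGT has 12 scheduled post-baseline visits. With change and percent change in two analysis sets that makes 12 x 2 x 2 = 48 comparisons, each of which can end up on a different method.

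What is at stake is how precisely the AGT reduction is reported, which is what a reader of this biomarker study would carry forward.

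**Working it through.** **The plan's own figure.** There is none to reproduce. The visible text gives no SD by arm, expected reduction, power or planned interval. The basis for the sample size is not visible, which is not treated as a fault.

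**Inputs from the documents.** About 30 subjects at 2:1 gives 30 x 2/3 = 20 active and 10 placebo. Tests are 2-sided at 5% (SAP 3.1). Treatment plus a two-level stratum leaves 30 - 3 = 27 residual degrees of freedom.

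**Assumed inputs.** Placebo SD of percent change 15 points; true reduction g of 30%, 50% or 70%; between-subject SD of response, t, from 0 to 20 points; Shapiro-Wilk cut-off p < 0.05.

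**Step 1: spread in the active arm.** SD(active) = sqrt[(15(1 - g))² + t²]. With t = 0 and g = 50% this is 7.5, so the placebo/active SD ratio is 2. The two SDs are equal when t = 15 x sqrt[1 - (1 - g)²], that is 10.7, 13.0 and 14.3 points for g = 30%, 50% and 70%.

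**Step 2: pooled against true standard error.** The pooled variance is s² = (19 x SD(active)² + 9 x SD(placebo)²)/28. The pooled SE is sqrt[s²(1/20 + 1/10)]. The true SE is sqrt[SD(active)²/20 + SD(placebo)²/10].

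For g = 50% and t = 0:
- s² = (19 x 56.25 + 9 x 225)/28 = 110.5, so the pooled SE is sqrt(110.5 x 0.15) = 4.07.
- The true SE is sqrt(56.25/20 + 225/10) = 5.03.
- The ratio is 0.81.

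**Step 3: coverage of a nominal 95% interval from the SAP model**, simulated with two balanced strata.

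| Reduction | Response SD (t) | Active SD | Pooled SE / true SE | Coverage |
|---|---|---|---|---|
| 30% | 0 | 10.5 | 0.89 | about 91% |
| 50% | 0 | 7.5 | 0.81 | 88-89% |
| 70% | 0 | 4.5 | 0.74 | 85% |
| 50% | 8 | 11.0 | 0.90 | about 92% |
| 50% | 12 | 14.2 | 0.98 | about 95% |
| 50% | 14 | 15.9 | 1.02 | about 95% |
| 70% | 14 | 14.7 | 0.99 | about 95% |
| 50% | 20 | 21.4 | 1.12 | about 97% |

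A Welch interval covers 94-96% across these cases. With log-normal data it covers 93.3-94.8%. If the Per Protocol Set fell to 18:8 (an assumption), the SE ratio at a placebo/active SD ratio of 2 would be 0.78 instead of 0.81.

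**Step 4: the normality gate.** Shapiro-Wilk falls below 0.05 in about 5% of trials with normal data and equal SDs. With proportional error it does so in about 14-18% at a 50% reduction and about 45% at 70%. With log-normal data and a log-scale SD of 0.35 the rates reach 37% and 54%. Passing the check does not protect the interval: among log-normal trials that pass, ANOVA coverage is 86-88% at a 50% reduction and 78-82% at 70%.

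**Step 5: the significance test.** If the drug does nothing to AGT, the two arms share one distribution, their SDs are equal, and the rejection rate is 5.2% in simulation. At reductions of 50% or more in the log-normal cases, the ANOVA rejects zero in at least 99.8% of trials.

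**Step 6: width after the change** (active SD 10 points).

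| Placebo/active SD ratio | ANOVA width | Welch width | Change |
|---|---|---|---|
| 0.5 | 13.69 | 11.15 | 19% narrower |
| 1 | 15.68 | 16.04 | 2% wider |
| 2 | 21.87 | 28.56 | 31% wider |
| 3 | 29.44 | 42.25 | 44% wider |

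**The case against.** The strongest reply is that the direction of the error is not documented. No SD by arm is visible, and a more variable placebo arm follows only if subjects respond nearly alike. A response SD of about 11-14 points brings coverage back to about 95%, and a larger one makes the interval too wide. This stands: a reader might infer that the plan's error bars will be too narrow, and the documents do not support that.

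Second, the SAP promises no confidence interval for the difference, even under ANOVA, so no stated interval under-covers. This also stands. The coverage figures describe the interval that the specified model would produce, and the missing interval is part of the point.

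Third, a reader might infer an inflated false-positive rate, since equal means with an SD ratio of 2 reject in 11.6% of simulated trials. That case needs a drug that changes the spread of AGT but not its mean. With no effect on AGT the rate stays near 5%.

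Fourth, a reader might say that the effect estimate is lost after a switch. That goes too far: by-arm means, SDs and standard errors do not depend on the test. What is missing is a specified between-arm estimate with an interval.

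Fifth, the switch rates rest on an assumed 0.05 cut-off and on the assumed distribution. They show that a switch is a realistic possibility and do not predict how often it would happen.

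**Conclusion.** The point holds in a limited form. The plan fixes a pooled-variance model on a ratio-type endpoint with about 20:10 subjects, checks the wrong assumption for that risk, and may replace the model with a test for which no between-arm estimate or interval is specified. Nothing elsewhere in the documents repairs this.

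The size depends on unseen variability. Under a placebo SD of 15 points, coverage runs from 85% (70% reduction, purely proportional error), through about 95% when the SDs are similar, to about 97% when the active arm is clearly the more variable. An unequal-variance interval is close to 95% whichever applies, so the choice need not rest on guessing the direction. The conclusion that AGT falls is not in doubt for large effects. The precision attached to the estimated reduction is. This is a worthwhile and inexpensive improvement to the SAP and does not threaten the primary test.

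**What to change.** In SAP 3.5.1 and protocol 10.6.3:

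- Keep percent change as the primary endpoint and keep treatment and stratum in the model. Allow a separate residual variance per arm with Satterthwaite degrees of freedom, and report the treatment difference with a 95% CI.
- Make this the fixed primary method at every visit and remove the Shapiro-Wilk gate.
- Always report van Elteren as a sensitivity analysis, with a stratified Hodges-Lehmann shift and its CI.
- Optionally add ln(Day 43 AGT / baseline AGT), back-transformed, as a further sensitivity analysis. State that it estimates a ratio of geometric means and not the mean percent change.

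The cost is SAP wording, one model option and one extra estimator. The interval becomes about 30-45% wider when placebo is much the more variable arm, changes little when the SDs are similar, and narrows when the active arm is the more variable. The simulated comparison used a Welch interval without the stratum term. The model proposed here adds that term and was not simulated separately, so a short check before the SAP is finalised would be sensible.

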10. STATISTICAL CONSIDERATIONS

10.1. Stratification

Subjects will be stratified based on screening plasma AGT concentration (≤ 30 $\mu\text{g/mL}$ vs. > 30 $\mu\text{g/mL}$).

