10.6.3. Efficacy Analysis

The primary analysis will be the comparison of percent change from Baseline to Study Week 7 (Study Day 43) in plasma AGT between ISIS 757456 80 mg group and placebo group in the Per Protocol Set. The data will be analyzed using analysis of variance (ANOVA) with treatment and randomization stratification factor (screening AGT concentration) as independent variables. In the case data departs substantially from normality, the nonparametric van Elteren test will be employed instead.

The secondary efficacy analyses will be performed in a similar way to the primary analysis, which include:

- Comparison of change and percent change from Baseline to each schedule post-Baseline visit in AGT between ISIS 757456 80 mg group and placebo group in PPS and FAS
- Comparison of change from Baseline to each schedule post-Baseline visit in in-clinic SBP and DBP between ISIS 757456 80 mg group and placebo group in PPS and FAS

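### The AGT models adjust for a two-level screening stratum but not for continuous baseline AGT; the possible loss of efficiency is modest and falls mainly on the secondary absolute-change comparison

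*Combined protocol and SAP*

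**What the plan says.** Protocol 10.6.3 and SAP 3.5.1 give the same primary model, in the SAP's words: "The data will be analyzed using analysis of variance (ANOVA) with treatment and randomization stratification factor (screening AGT concentration) as independent variables". The comparison is of "plasma AGT between ISIS 757456 80 mg group and placebo group in PPS", and the endpoint (SAP 1.3.1) is "Percent change in plasma angiotensinogen from Baseline to Study Day 43 (Week 7) compared to placebo". If normality fails, both documents switch to the van Elteren test, which is stratified and takes no continuous covariate.

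SAP 3.5.2 extends the approach: "The secondary efficacy analyses will be performed in a similar way to the primary analysis". Its list begins with "Comparison of change and percent change from Baseline to each schedule post-Baseline visit in AGT", in both PPS and FAS.

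The factor in the model is the randomization stratum. Protocol 10.1 says "Subjects will be stratified based on screening plasma AGT concentration", with one cut at 30 µg/mL. The baseline in the endpoint is a different quantity. SAP 3.1 says "The baseline for plasma AGT will be define as the average of all values on or after Study Day -7" and before the first dose. No visible AGT model, fallback or sensitivity analysis contains that continuous baseline.

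**The concern.** The stratum is a coarse and early stand-in for baseline.

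- **Timing.** Appendix A places the screening sample between Day -42 and Day -22, while subjects still take an ACE inhibitor or ARB plus one other agent (protocol 5.1, criterion 9). The baseline samples, at Day -7 and Day 1 pre-dose, come after those medications are withdrawn.
- **Coarseness.** Entry requires at least 20 µg/mL, so one stratum covers 20 to 30 and the other has no upper limit. Differences within a stratum stay in the error term.

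Baseline can predict the outcome in two ways. Measurement noise in baseline enters both change and percent change, which induces a negative correlation with baseline in both arms. Also, if the drug lowers AGT proportionally, the change in µg/mL grows with baseline in the active arm.

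What is at stake is interval width, and how far a chance baseline difference between two small arms moves the estimate. The analysed number may be below 30: the primary set is per protocol, withdrawn subjects are not replaced (protocol 4.3), and missing values are not imputed (SAP 3.3.2).

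**Working it through.** **Inputs from the documents.** About 30 subjects (protocol 3.3), allocated 2:1 (protocol 3.1), hence about 20 versus 10; two-sided 5% tests (SAP 3.1). The ANOVA has 30 - 3 = 27 residual degrees of freedom, or 26 with baseline added. The plan shows no power figure to reproduce, because the sample-size text is not visible.

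**Break-even.** Let r be the correlation of baseline AGT with the outcome, given treatment and stratum. The variance of the adjusted treatment estimate relative to the planned one is (1 - r²)(1 + 1/25).

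| r | variance ratio |
|---|---|
| 0 | 1.00 × 1.04 = 1.04 |
| 0.2 | 0.96 × 1.04 = 1.00 |
| 0.3 | 0.91 × 1.04 = 0.95 |
| 0.4 | 0.84 × 1.04 = 0.87 |
| 0.5 | 0.75 × 1.04 = 0.78 |

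Break-even is r = √(1 - 1/1.04) = 0.196. It rises to 0.21 with 27 subjects analysed and 0.22 with 24.

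**Plausible r (assumed inputs).** Simulations used lognormal AGT with median 28 µg/mL, between-subject log SD 0.2 to 0.3, within-subject 0.10 to 0.20, mostly 30% or 50% reductions, entry at 20, stratified 2:1 allocation and a two-value baseline. One set of twelve settings, 1,500 trials each and including no effect, gave:

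- percent change: mean r -0.11 to -0.37, variance ratio 0.88 to 1.03;
- absolute change: mean r -0.21 to -0.53, variance ratio 0.80 to 0.97.

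Two further sets of twelve assumed settings widen these ranges to 0.88 to 1.06 and 0.75 to 1.01.

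**Power for percent change.** At a true difference of 1.125 residual SDs the ANOVA has 80.0% power. Adding baseline gives 78.3% at r = 0 and 82.0% at r = 0.3. At 2 SDs, power is at least 99.8% under either model. In one of the simulation sets the mean t for percent change was about 3.4 to 17, so power was already high.

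**Chance imbalance.** Without stratification, the SD of the standardized baseline difference is √(1/20 + 1/10) = 0.387. With stratification the simulations give about 0.26 to 0.37. Imbalance reaches the estimate only through r. A one-SD imbalance of 0.37 with r of 0.1 to 0.3 moves it by roughly 0.04 to 0.11 outcome SDs, against a standard error of about 0.39.

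**Absolute change and the common slope.** Under a purely proportional reduction p with a noise-free baseline, the slope of change on baseline is -p on active and 0 on placebo. In units of the baseline variance, the baseline part of the variance of the estimate is p²/20 without adjustment. A pooled slope is about (20/30)(-p) = -2p/3. This leaves (p/3)²/20 + (2p/3)²/10 = p²/180 + 8p²/180 = p²/20, which is no gain. A simulation with within-subject log SD 0.02 and a 50% reduction agrees (ratio 1.03). The gain from a common slope therefore comes largely from baseline noise (regression to the mean). In 7 of 12 simulated settings the common-slope model also reported only 0.72 to 0.88 of the true variance for absolute change.

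**The case against.** The strongest reply is that the planned model matches the stratified randomization and is valid, and that percent change already divides by baseline. Both statements stand. Imbalance in baseline is random error that the standard error already counts, and stratification reduces it.

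A reader might infer that precision is definitely lost in the headline comparison, or that the primary test gives up substantial power. The documents do not support either. They show no SD, effect or correlation. A sizeable power gain would need a correlation near 0.5, together with an effect small enough that power is still in question. The simulated mean correlations for percent change stop at 0.37 in magnitude, and effects of the assumed size leave little power to gain.

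It is also fair that a proportional reduction alone does not justify a common-slope model for absolute change at 2:1, and that such a model can report intervals that are too narrow. This changes the form of the remedy.

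What survives is that a better covariate than the stratum is collected and unused in every visible AGT model. Choosing an adjusted model only after an imbalance has been seen would be worse than fixing one in advance.

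**Conclusion.** The point holds as one of efficiency and robustness, and mainly for the secondary absolute change in AGT, where the variance reduction is about 0 to 25%. For the primary percent change the result is roughly neutral: from a slight loss to about a 12% reduction, with break-even at a partial correlation near 0.2.

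These ranges depend on the assumed variabilities, the assumed reductions and an analysed sample close to 20 versus 10. The plan is not in error, and nothing here calls the validity of the primary test into question. Adjustment is nevertheless worth prespecifying: it costs little, and it settles the handling of chance imbalance before the data are seen.

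**What to change.** 1. **SAP 3.5.2, absolute change in AGT.** Add continuous baseline AGT as defined in SAP 3.1, centred, to treatment and stratum. Include a treatment-by-centred-baseline term or use heteroscedasticity-robust standard errors, because a proportional reduction makes slopes and variances differ by arm at 2:1. Robust errors are the safer of the two: the interaction term lets the slopes differ but still pools residual variance across arms.
2. **SAP 3.5.1 and protocol 10.6.3, percent change.** Prespecify the same baseline-adjusted model and state in advance which analysis is primary.
3. Report the planned ANOVA alongside in each case, and leave the van Elteren fallback as it is.

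The cost is a few lines of SAP text and code, plus one residual degree of freedom (two with the interaction). If baseline proves unrelated to the outcome, power falls by about 1 to 2 points, or slightly more with the interaction.
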